**(5) Data Collection Methods, Assessments, Interventions and Schedule (what assessments performed, how often)**

This randomized, partially double-blinded study will involve three study visits as well as home questionnaires, urine and stool collection, and diet assessment by a Registered Dietitian. The first study visit is in conjunction with a scheduled outpatient clinic appointment for follow-up of celiac disease. There will be additional visits with the study coordinator at randomization (week 8) and study completion (week 30). The interval between the first and second study visits is a run-in period to allow for behavior modification in response to the clinician assessment and/or participation in a study where adherence will be monitored. A dietitian assessment will be conducted by a Registered Dietitian at randomization (week 8) and at the end of the study (week 30). At each study visit, participants/caregivers will be asked to complete symptom and quality of life questionnaires. Blood may be collected and stored for testing for biomarkers of gluten-free diet adherence, celiac disease activity and nutrition at the initial and final study visits. Throughout the study period, participants will maintain a diary of suspected and probable gluten exposures.

During weeks 2 through 7 (between the first and second study visits), when prompted by the study coordinator, participants will collect their next urine at home and to complete the symptom questionnaire. Participants will be blinded to the exact timing of sample collection. This method will be employed throughout the study period to ensure that sample collection reflects usual behavior and to reduce the Hawthorne Effect due to participants adjusting their eating behaviors in anticipation of observations being collected.

During week 8, participants will bring samples collected at home and completed questionnaires to the second study visit along with an additional stool sample taken at the week 8 time point. At this time, there will be a blood draw and participants will be randomized to continue with double-blinded test results or an open results arm. Randomization will be stratified based upon the results of GIP testing in stool collected at week 8 to ensure that participants with documented gluten exposure are distributed equally between the blinded and open results arms. Participants in the open results arm will receive instruction in using home test kits for detection of GIPs and supplied with test kits to be used at home during the remainder of the study period. Participants will be given a parking voucher and receive a \$30 ClinCard as a token of appreciation. All participants will also have a diet assessment by a Registered Dietitian either in person or remotely by telephone or video link in conjunction with the week 8 study visit.

During weeks 8 through 30, participants will keep a diary of any suspected gluten exposures. Participants will be contacted by the study co-ordinator at random intervals (approximately every three to four weeks) and instructed to collect their next urine and complete the symptom questionnaire. Participants in the open results arm will also perform home testing and send a photo of the test results to the study co-ordinator to document results and confirm test completion. Used test kits may be disposed in household trash. Participants will also test up to 4 stool samples during this time that will be collected and tested at the discretion of the participant. Participants will report date of use, results,

and reason for use after each home stool test. Participants will return all other study materials and containers at the final study visit.

At week 30, participants will have a final study visit with the study co-ordinator to return urine samples collected at home. An optional blood draw will be performed for testing for markers of gluten-free diet adherence and celiac disease activity and participants/caregivers will be asked to complete a questionnaire with items pertaining to symptoms and quality of life. All participants will also have a diet assessment by a Registered Dietitian either in person or remotely by telephone or video link in conjunction with the week 30 study visit. Participants will receive a parking voucher and \$30 on their ClinCard as a token of appreciation. Participants in the open arm will be instructed to report all unused stool test kits. Participants in the blinded arm will be given up to 4 test kits to keep at this visit as a token of appreciation for completing the study.

All participants will be informed of the results of their urine sample used for stratification at the final study visit. Participants in the blinded arm will be contacted and notified of results of testing for biomarkers of gluten-free diet adherence (GIPs) once this has been completed. Disclosure of test results to treating providers will be at the discretion of participants.

#### **(6) Study Timeline (as applicable)**

- Eligibility Screening
  - Participants who are eligible for this study will be identified when they are scheduled for an outpatient clinical appointment for follow-up of celiac disease
  - Potential participants will be contacted and informed of the study. If they express that they may be interested in participating, they will be asked to provide verbal consent to receive sample collection materials and a copy of the consent form.
  - urine sample (from a first morning void if possible) will be collected. Optional stool sample collected.
- Recruitment Visit (week 1) in conjunction with a scheduled outpatient clinic appointment for follow-up of celiac disease
  - written informed consent
  - provide stool and urine samples (may be collected prior to visit)
  - patient/parent self-report questionnaire
  - height and weight
  - blood draw: TTG, DGP, CBC, stored samples for makers of gluten-free diet adherence, celiac disease activity and nutrition.
  - Participant receives a parking voucher
- At home (weeks 1 through 7)
  - collect additional urine samples and complete questionnaire when contacted by study coordinator at random intervals (x2)
  - keep a diary of suspected/probable gluten exposures.
  - collect an additional stool sample during week 8 (to be used at week 8 study visit for randomization)
- Study Visit 2: (week 8)
  - Return samples and questionnaires completed at home when prompted.
  - Bring additional stool sample collected during week 8 (for randomization)
  - Randomization to blinded or open test results.
  - patient/parent self-report questionnaires
  - height and weight
  - Participant receives parking voucher and \$30 ClinCard as a token of appreciation
  - Diet assessment, either in person or remotely by telephone or video link
- At home (weeks 8 through 30)
  - collect additional urine samples and complete questionnaire when contacted by study coordinator at random intervals (x6, approximately every four weeks)
  - keep a diary of suspected/probable gluten exposures
  - Use of stool kits at participants discretion (x0-4)

- Final study visit (week 30)
  - Return samples and questionnaires completed at home.
  - Complete quality of life and symptom questionnaires.
  - Diet assessment, either in person or remotely by telephone or video link.
  - Height and weight
  - Optional blood draw: TTG, DGP, CBC, stored samples for markers of gluten-free diet adherence, celiac disease activity and nutrition.
  - Participants informed of results of sample used for stratification.
  - Participant is given parking voucher and \$30 ClinCard as a token of appreciation
  - Blinded participants given test kits (x4) as a token of appreciation
- All participants will be unblinded and notified of results once the samples are processed.

## **E. Adverse Event Criteria and Reporting Procedures**

All subjects who participate and have a subsequent safety evaluation will be included in the safety analyses. All adverse events reported during the study will be listed, documenting course, severity, and outcome. Laboratory parameters, vital signs, and physical exam results will be summarized with descriptive statistics as appropriate.

## **F. Data Management Methods**

All study participants will be assigned a unique study identifier which will be used to link all study data (lab results, anthropometrics, questionnaire responses, etc). The master list of subject names and study IDs will be stored and locked in a file cabinet in the research office. Only study staff will have access to this list. All other samples will be labelled with the date, patient initials and study ID number. All labs collected for clinical purposes at the time of study blood draw will be labelled with the patient's name, medical record and DOB, processed per standard procedure through the laboratory department and entered into the medical record as these are clinically relevant to patient care. This will include samples for EMA and TTG at scheduled clinic visits. All other study-related labs will be labelled with the study ID, processed without identifying information and will not be entered into the medical record. All data (lab results, pathology results and survey results) will be indexed using the study ID and collated in a REDCap database administered by Boston Children's Hospital.

## **G. Quality Control Method**

Study investigators will oversee data entry and will follow progress to assure accuracy of the data. All weight and height measurements will be obtained by trained staff. Equipment to measure quantitative levels of GIPs will be calibrated regularly according to the manufacturer protocol.

## **H. Data Analysis Plan**

For all outcomes, descriptive data analysis will be used to assess variables' distributions and to detect outliers and influential observations. We will estimate means (and standard deviations) and medians (and interquartile ranges) of continuous variables, and proportions of categorical variables. In addition, we will examine the data using plots, such as boxplots, histograms and smoothed-scatterplots. When necessary, variables will be transformed to meet assumptions for statistical tests. All statistical tests will be two-sided and will use a Type I error of 5%. For confidence intervals, we will use two-sided 95% coverage probabilities.

As a general approach, all proportions will be reported as mean with the associated 95% confidence interval for the estimate. This will provide more meaningful information about the precision of each estimate as well as the possible clinical significance of any observed differences in the mean value. As such, p values for comparisons of means will not be determined with the implicit assumption that values for which the 95% confidence intervals overlap do not differ significantly. Relationships between continuous measures will be analyzed using Pearson's correlation coefficient. Where appropriate,

continuous measures will also be converted to categorical variables (e.g., serum antibody negative/positive vs. GIP negative/positive).

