#### *Primary outcome*

For the primary outcome, gluten exposure is defined as percentage of samples collected between weeks 8 and 30 with detectable gluten immunogenic peptides using the quantitative assay. Differences in gluten exposure between the blinded and open results groups will be assessed using the chi-squared test.

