### **I. Statistical Power and Sample Considerations**

The primary outcome is the difference in rate of gluten detection in the six urine samples provided after randomization (weeks 8 through 30) between the blinded and unblinded groups. A total sample of 102 (n=51 in each group) provides 90% power to detect a difference of 50% gluten detection in the blinded group versus 25% gluten detection in the open results group, given six outcomes per participant with an intraclass correlation of 0.6 and alpha set at 0.05. Given a more conservative intraclass correlation of 0.8, we will still have 82% power to detect the predicted effect size. If participants are more highly adherent, then this sample size should also be sufficient as fewer participants will be required. For example, using the same assumptions for intraclass correlation, with 43 subjects in each group there is 90% power to detect a difference of 40% gluten detection in the blinded versus 25% gluten detection in the open results group (alpha = 0.05).

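### The rule that overlapping 95% confidence intervals mean no significant difference tests two arms at about 0.6% rather than the stated 5%, and conflicts with the tests named for individual outcomes

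*Protocol*

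**What the plan says.** All the statements are in the current protocol.

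- Section H, first paragraph: "All statistical tests will be two-sided and will use a Type I error of 5" (that is, 5%), and "For confidence intervals, we will use two-sided 95% coverage probabilities".
- Section H, second paragraph: "As a general approach, all proportions will be reported as mean with the associated 95% confidence interval for the estimate". It then concludes that mean comparisons get no p value, the assumption being that "values for which the 95% confidence intervals overlap do not differ significantly".
- Section H, Primary outcome: "Differences in gluten exposure between the blinded and open results groups will be assessed using the chi-squared test".
- Section H, Secondary outcomes: group comparisons of symptom and quality-of-life scores use a t-test, described as paired. No between-arm test is named for mean peptide concentration or for growth.
- Section D(4): the primary measure is each child's percentage of positive samples after randomization, averaged over children. Mean peptide concentration in the two arms is listed as a secondary outcome.
- Section I: "A total sample of 102 (n=51 in each group) provides 90% power" for 50% versus 25% detection, with six urine samples per child, an intraclass correlation of 0.6 and alpha 0.05. With a correlation of 0.8 the stated power is 82%.

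**The concern.** Non-overlap of two separate intervals is a stricter requirement than significance of the difference. The interval half-widths add directly, whereas the standard error of a difference between independent estimates adds in quadrature. Reading overlap as no difference therefore tests well below the nominal level, and real differences between the arms would be reported as not significant.

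Section H also gives two criteria that can disagree on the same data: a 5% test, and overlap. A t-test on mean scores cannot sit beside a statement that comparisons of means get no p value. With no order of precedence, the choice between the two could be made after the results are known.

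**Working it through.** **Inputs.** Two-sided alpha 0.05 and 95% intervals (section H). From section I: 51 children per arm, six samples each, 50% versus 25%, intraclass correlation 0.6 or 0.8.

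**1. Reproduce the stated power.** Design effect = 1 + (6 − 1) × ICC; effective n per arm = 51 × 6 / design effect. Pooled-variance test of two proportions:

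- ICC 0.6: design effect 4, effective n = 306/4 = 76.5, power 89.9% (stated 90%).
- ICC 0.8: design effect 5, effective n = 306/5 = 61.2, power 82.3% (stated 82%).

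Both reproduce, so the planned power presumes a 5% test.

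**2. What the overlap rule requires.** Two 95% intervals fail to overlap when |difference| > 1.96 × (SE1 + SE2). A 5% test of independent arms needs |difference| > 1.96 × √(SE1² + SE2²). On the Z scale the overlap rule's critical value is 1.96 × (SE1 + SE2) / √(SE1² + SE2²), which with equal standard errors is 1.96 × √2 = 2.772.

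**3. Type I error.** 2 × (1 − Φ(2.772)) = 0.0056, or 0.56%.

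**4. Power of a comparison that has 90% at the 5% level.** Φ(1.960 + 1.282 − 2.772) = Φ(0.470) = 68.1%.

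**5. Robustness.**

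| Setting | Type I error | Power (90% at 5%) |
|---|---|---|
| Equal SEs, normal | 0.56% | 68.1% |
| Equal SEs, t with 51 per arm | 0.55% | 66.7% |
| Simulation, 100,000 trials, 51 per arm | 0.59% | 66.9% |
| SE ratio 1.5 | 0.66% | 70.0% |
| SE ratio 2 | 0.85% | 73.0% |

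In the same simulation the ordinary t-test gave 5.2% and 90.0%.

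**6. The primary outcome's planning rates, if the rule applied there.**

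- ICC 0.6: SE1 = √(0.25/76.5) = 0.0572; SE2 = √(0.1875/76.5) = 0.0495; SE of the difference = 0.0756. A 5% test needs a difference of 1.96 × 0.0756 = 0.148; non-overlap needs 1.96 × 0.1067 = 0.209. Power under overlap = Φ((0.25 − 0.209)/0.0756) = 70.6%, against 91.1% for the z-test with the same unpooled variances.
- ICC 0.8: SE1 = 0.0639; SE2 = 0.0553; SE of the difference = 0.0845. Non-overlap needs 0.234. Power = 57.6%, against 84.1%.

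With the ICC 0.6 standard errors, an observed difference between about 15 and 21 percentage points would be significant by the 5% test and not different by the overlap rule.

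**The case against.** The strongest reply is that a specific instruction outranks a general one. The overlap sentence belongs to a general approach, while the primary outcome has its own subsection with a chi-squared test and a sample size set at alpha 0.05. Symptom and quality-of-life scores likewise have a named test. On that reading the primary outcome loses no power. This stands as a limit on scope. A reader might infer that the rule cuts the trial's 90% power to 68%, because section D(4) makes the primary measure an average over children and so a mean. The documents do not support that as a fact: the primary analysis text speaks of a percentage of samples and names a chi-squared test, and section I speaks of a detection rate. They leave the matter unclear, and nothing says that the general approach overrides the named test.

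It can also be said that the error is conservative, and that readers could rebuild an interval for the difference from published per-arm intervals. Both are true, but the trial's own conclusions would still follow the wrong criterion, and the bias runs only towards finding no effect.

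The sentence is awkward and could be parsed as rejecting the overlap assumption. The preceding sentences offer confidence intervals as the more informative report, so the natural reading is that they replace p values and that overlap is read as no difference.

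Finally, a statistical analysis plan that is not shown may name further tests. The finding does not depend on their absence: the protocol states a criterion that is wrong and contradicts its own 5% level.

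**Conclusion.** The overlap rule is wrong as written and inconsistent with the rest of section H. For two independent arms with similar standard errors it tests at about 0.6% two-sided instead of 5%. Equal allocation makes similar standard errors a fair assumption, and a ratio of 2 raises the level only to 0.85%.

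The firm consequence concerns between-arm means with no named test: mean peptide concentration, and growth if it is compared between arms. There, overlap is the protocol's only stated criterion, and a comparison with 90% power at 5% would have about 68%. The protocol gives no power for these outcomes, so 68% shows the size of the loss and is not a forecast for any one of them.

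For the primary outcome the consequence is conditional. If the overlap rule governed it, power would be about 71% (ICC 0.6) or 58% (ICC 0.8) at the planning rates, against the stated 90% or 82%. If the chi-squared test governs, the overlap rule costs it nothing. The equal-standard-error figure of 68% should not be quoted as the power of the primary comparison.

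**What to change.** In section H:

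- Delete the sentence that withholds p values and reads overlap as no significant difference.
- State that the two-sided 5% analyses given for each outcome prevail over the general approach, so that the primary outcome's criterion is no longer in doubt.
- For every between-arm comparison, report the estimated difference with its own 95% confidence interval and base the conclusion on whether that interval excludes zero. A p value may be added but is not needed for the decision.
- Keep per-arm estimates and intervals as description only.

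The cost is a few sentences of wording, with no extra data or participants. The change also serves the section's stated wish to show precision and clinical relevance, since the interval for the difference shows both directly. Keeping the overlap rule at 90% power would instead need about ((2.772 + 1.282)/(1.960 + 1.282))² = 1.56 times the sample size.

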#### *Primary outcome*

For the primary outcome, gluten exposure is defined as percentage of samples collected between weeks 8 and 30 with detectable gluten immunogenic peptides using the quantitative assay. Differences in gluten exposure between the blinded and open results groups will be assessed using the chi-squared test.

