#### **(4) Definition of Primary and Secondary Outcomes/Endpoints**

##### Primary outcomes:

- Difference in frequency of gluten exposure following randomization in blinded vs. open results groups. Gluten exposure is defined as the average per individual subject post-randomization percentage of samples collected between weeks 8 and 30 with detectable gluten immunogenic peptides using the quantitative assay.

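### The primary chi-squared test makes no allowance for six correlated urine results per child; at the plan's own ICCs its type I error is about 33–38%, not 5%

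*Protocol*

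**What the plan says.** Three parts of the protocol describe the primary comparison.

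- **Section D(4), Primary outcomes**, works per child: "Gluten exposure is defined as the average per individual subject post-randomization percentage of samples collected between weeks 8 and 30" with a detectable result on the quantitative assay.
- **Section H, Primary outcome**, omits the per-child step: "gluten exposure is defined as percentage of samples collected between weeks 8 and 30 with detectable gluten immunogenic peptides using the quantitative assay". It then names the test: "Differences in gluten exposure between the blinded and open results groups will be assessed using the chi-squared test".
- **Section I** bases the sample size on repeated results within a child. "A total sample of 102 (n=51 in each group) provides 90% power" to detect 50% against 25% detection, "given six outcomes per participant with an intraclass correlation of 0.6 and alpha set at 0.05". It adds: "Given a more conservative intraclass correlation of 0.8, we will still have 82% power to detect the predicted effect size".

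The general part of Section H sets a two-sided 5% type I error for all tests. Nowhere does the protocol give, for the primary outcome, a clustering adjustment, a GEE or mixed model, or a rule that reduces each child to a single yes/no result.

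**The concern.** An ordinary chi-squared test on samples requires the samples to be independent. Six urines from one child are not, and Section I says so by assuming an ICC of 0.6 to 0.8. The test in Section H therefore fits neither the endpoint in D(4), whose unit is the child, nor the power calculation in Section I, which discounts the samples for correlation.

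The trial's main conclusion is at stake. A test that overstates the information by a factor of four or five gives p-values that are far too small. A confidence interval computed on the same basis would be far too narrow. A chance difference between arms could then be reported as an effect of showing families their results, in either direction.

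**Working it through.** **Inputs, all from the protocol.** 51 children per arm, 6 post-randomization urine samples each, ICC 0.6 (conservative 0.8), detection 50% against 25% (Section I); two-sided alpha 0.05 (Section H).

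**Step 1: design effect.** DE = 1 + (6 − 1) × ICC. Samples per arm = 51 × 6 = 306.

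- ICC 0.6: DE = 4.0, effective samples per arm = 306/4 = 76.5
- ICC 0.8: DE = 5.0, effective samples per arm = 306/5 = 61.2

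**Step 2: reproduce the stated power.** Two-proportion normal formula with pooled null variance and no continuity correction:

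power = Φ[(0.25 − 1.96 × √(2 × 0.375 × 0.625/n)) / √((0.25 + 0.1875)/n)]

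- n = 76.5: (0.25 − 1.96 × 0.0783)/0.0756 = 1.277, power 89.9% (stated 90%)
- n = 61.2: (0.25 − 1.96 × 0.0875)/0.0845 = 0.928, power 82.3% (stated 82%)

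The stated figures are recovered with the design effect. With n = 306, the number an unadjusted test would use, the same formula gives (0.25 − 1.96 × 0.0391)/0.0378 = 4.58, or power above 99.9%. Section I thus rests on an analysis that allows for clustering.

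**Step 3: type I error of the unadjusted test on pooled samples.** The true variance of the difference is DE times the variance the test assumes, so true alpha = 2 × [1 − Φ(1.96/√DE)].

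| ICC | DE | 1.96/√DE | True two-sided alpha |
|---|---|---|---|
| 0.1 | 1.5 | 1.600 | 11.0% |
| 0.2 | 2.0 | 1.386 | 16.6% |
| 0.4 | 3.0 | 1.132 | 25.8% |
| 0.6 | 4.0 | 0.980 | 32.7% |
| 0.8 | 5.0 | 0.877 | 38.1% |

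A confidence interval computed on the same independence assumption has 1/√4 = 50% of the correct width at ICC 0.6 and 1/√5 = 45% at ICC 0.8.

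**Step 4: simulation.** 20,000 trials per setting, 51 children per arm, six samples each, no difference between arms, common detection rate 25%, 37.5% or 50%.

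| Analysis | ICC 0.6 | ICC 0.8 |
|---|---|---|
| Pooled chi-squared, two correlation models | 31.7–33.3% | 37.6–38.7% |
| Pooled chi-squared with continuity correction, beta-binomial | 30.1–31.4% | 35.4–36.2% |
| t-test on each child's fraction positive, beta-binomial | 4.9–5.1% | 4.8–5.2% |

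Under the design alternative (50% against 25%), the t-test on per-child fractions has 89.9% power at ICC 0.6 and 82.1% at ICC 0.8. These are the figures Section I promises.

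**The case against.** The best reply is that the protocol never says in words that samples will be pooled as independent. The authors plainly knew about the correlation, since they built it into Section I. They may have meant an ICC-adjusted chi-squared test, or a chi-squared test on one categorical result per child. Section H allows continuous measures to be made categorical where appropriate. In the simulation, an any-positive yes/no result per child kept the error at about 5–6%. A statistical analysis plan, not at hand, might also settle the method.

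Part of this stands. The 33–38% applies to the pooled reading, with all six samples returned and the planning ICCs true. With four samples per child at ICC 0.6, DE = 1 + 3 × 0.6 = 2.8 and the error is about 24%. Nor is a chi-squared test wrong in principle: with an explicit ICC adjustment it would be acceptable.

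It does not rescue the text. Section H defines the variable as a percentage of samples, so pooling is the plain reading. No adjustment or per-child category is stated for the primary outcome; the categories Section H does spell out, for change in exposure, belong to a secondary outcome. An any-positive rule would depart from D(4) and from the detection rates used in Section I. The test is named in the protocol, so it is not a detail left for later.

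Section H also says that comparisons of means will be judged by overlap of confidence intervals, not by p-values. That sits beside the named chi-squared test and does not cure the problem. If each arm's interval ignored clustering, non-overlap corresponds to a threshold of 2 × 1.96/√2 = 2.77. The false-positive rate would then be 2 × [1 − Φ(2.77/√DE)] = 16.6% at ICC 0.6 and 21.5% at ICC 0.8.

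**Conclusion.** The primary analysis is wrong as stated and must be corrected. The named test matches neither the per-child endpoint in D(4) nor the clustered sample-size basis in Section I. Run on pooled samples, its type I error is 32.7% (ICC 0.6) to 38.1% (ICC 0.8), six to eight times the nominal 5%. This assumes six returned samples per child and the protocol's own ICCs. Fewer samples or a lower ICC reduce the inflation, but it stays material: 11.0% even at ICC 0.1. The mismatch between the three sections holds whatever the ICC turns out to be.

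**What to change.** In Section H, replace the primary-outcome paragraph so that it uses the D(4) definition and takes the child as the unit of analysis. Either of these would do:

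- compare each child's fraction of positive post-randomization samples between arms, by linear model or two-sample t-test. This is closest to D(4), because each child counts equally; or
- fit a binomial GEE clustered on child, with robust standard errors corrected for small samples.

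Report the difference in percentage points with its 95% confidence interval from the same analysis, and remove the unadjusted chi-squared sentence. If the sponsor prefers to keep a chi-squared test, the ICC adjustment has to be written out. The paragraph should also name the specimens counted: Section I speaks of six urine samples, D(4) and Section H only of samples.

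The cost is one paragraph of wording. No extra data, visits or participants are needed, because the 51 per arm already allow for clustering.
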